# Hyperglycemia:

If hyperglycemia develops, defined as serum glucose levels >250mg/dL, other sources of hyperglycemia should be considered and addressed (sepsis). A minimum dosage reduction of 25% will occur. Blood sugars will continue to be monitored closely with additional adjustments as warranted.

# Coagulopathy:

Other sources of coagulopathy should be considered and addressed (sepsis, worsening liver failure). Omegaven administration will be reduced or halted. Coagulation profiles will continue to be monitored closely with additional adjustments as warranted.

#### **Duration of Therapy**

Patients will complete the study when he/she is completely off PN; develops a contraindication for further use; or the patient/family requests to be removed from the study protocol.

In the event that a patient who has been listed for a liver or liver/intestinal transplant has an organ become available, the participation in this protocol will not preclude them from receiving the transplant. Omegaven® will not be administered post transplant.

In the event that a patient whose hepatic enzymes and serum bilirubin have normalized still requires parenteral fat emulsion after receiving Omegaven® for more than 6 months, their clinical course will be reviewed, and a decision will be made whether to continue the Omegaven® or rechallenge the patient with conventional therapy (Intralipid®).

# **Discontinuation of Therapy**

Patients will continue to be followed by the Nutritional Support Program (LCH Division of Gastroenterology) upon discontinuation of therapy with Omegaven® a minimum of 3 months after the treatment is stopped. In addition, patients will be contacted annually for 5 years following completion of the study, to ascertain growth, well being and PN dependency.

# **Resumption of Therapy**

In the event that a patient who has been off the protocol more than 3 months must receive intravenous fat emulsion, treatment with Omegaven® will resume only if the patient shows evidence of PN liver disease (elevations in direct bilirubin > 2 or pathology findings consistent with cholestasis). Otherwise, the patient will be treated with conventional lipid emulsion.

# **Definition of Primary and Secondary Outcomes/Endpoints**

The primary outcome is normalization of direct bilirubin to less than 0.4mg/dL by 9 months.

Seconday outcomes include:

- Omegaven® will prevent EFA deficiency as evidenced by normal EFA profiles on monthly evaluations
- The rate of triglyceride levels > 400 mg/dL with Omegaven® will be similar to that seen with PN administered with soy oil IFE (conventional emulsion, i.e., Intralipid®) as evidenced by baseline data and then weekly and monthly evaluations
- PN containing Omegaven® will be safe for patients with respect to the risk of unexpected bleeding/coagulopathies as evidenced by weekly and monthly evaluations

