#### SPECIFIC AIMS/OBJECTIVES

- To determine the impact of Omegaven® on reversal of conjugated hyperbilirubinemia
- To determine the impact of Omegaven® on the prevention of essential fatty acid deficiency
- To determine the impact of Omegaven® administration on serum triglyceride
- To determine the impact of Omegaven® administration on coagulation profiles

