Similarly, other investigators studied livers in a newborn pig model and showed that intravenous administration of fish oil, which consists primarily of omega-3 fatty acids, reduced parenteral nutrition-induced cholestasis.(22) However, the study was only 3 weeks in duration and long-term effects from administration of omega-3 fatty acids alone were not evaluated. In fact, the idea that one could remove an essential fatty acid from the standard regime of nutritional support by PN has not been accepted. It has been thought that reduction of an essential fatty acid, such as omega-6, during long-term therapy would result in fatty acid deficiency and deterioration of the health of the patient. The Children's Hospital Boston's experience to date, demonstrates that the use of Omegaven® as monotherapy does not result in the development of essential fatty acid deficiency and it can actually be used to as monotherapy to treat this deficiency state.

Preliminary Safety and Efficacy Data for Use of Omegaven® in Other Diseases

Omegaven® has been used for over 10 years as an adjunct to conventional fat emulsions. According to current data, an increase in the proportion of omega-3 fatty acids is thought to optimize nutrition in general, but in particular benefit patients whose underlying disease might benefit from an increase in omega-3 fatty acids. An adequate intake of omega-3 fatty acids results in anti-inflammatory and immunomodulatory effects that are protective in nature from inflammatory tissue damage, capillary permeability, and improved immunological resistance. It may also reduce the risk of thrombosis and increase microvascular perfusion due to its anti-aggregatory and vasodilatory effects.

In Europe and Asia, the use of parenteral omega-3 fatty acids has been used in the following adult patient populations (24-28):

- Post traumatic and post surgical patients
- Patients experiencing early stages of sepsis/SIRS
- Patients at risk of hyperinflammatory processes
- Patients with inflammatory bowel disease (Crohn's disease, ulcerative colitis)

- Patients with inflammatory skin diseases (psoriasis, atopic eczema)

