# Patient Selection and Inclusion/Exclusion Criteria

After the diagnosis of PN liver injury is made, patients who are followed by the Neonatology, Gastroenterology, Surgery, or the Critical Care Service in conjunction with the patient's primary physician will contact [name], and an evaluation will be performed. If the patient's parents or guardians agree to participate in the study, informed consent will be obtained. The history of present illness and past medical history will be reviewed with the guardian and pertinent demographic and medical information will be recorded on data collection forms. These forms will be used to record all laboratory results, nutritional history, and descriptions of any liver biopsies performed.

Though most patients receiving parenteral nutrition do not develop end stage liver disease, there is a small percentage of patients, typically infants and children on prolonged courses of parenteral nutrition, who do go on to develop fulminant liver failure. The study population of this protocol is limited to patients felt to fulfill the following conditions:

- a) The patient will be PN-dependent (unable to meet nutritional needs solely by enteral nutrition) and
- b) The patient will have significant hepatic dysfunction due to PN despite utilization of all conventional therapies (the patient must have failed standard therapies to prevent the progression of his/her liver disease including surgical treatment, cycling of PN, reduction/removal of copper and manganese from PN, advancement of enteral feeding, and the use of ursodiol).

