# **Details of Omegaven® Administration**

After baseline labs are obtained (Table II), therapy with Omegaven® will be initiated at a starting dose of 0.5gm/kg/day infused over 12-24 hours. After two days, the dose will be increased to 1 gm/kg/day, the goal dose. Omegaven® will be infused intravenously through either a central or peripheral catheter in conjunction with parenteral nutrition. The same standards of care provided to all patients receiving parenteral nutrition solution will be followed. Laboratory tests will be performed as detailed in Table 2. Growth will be tracked weekly. If additional fat calories are needed, they will be provided via the enteral route.

In the event that a patient is unable to achieve adequate calories parenterally and is unable to tolerate enteral feeds, it may be necessary to evaluate whether or not the patient should continue the study with Omegaven® as monotherapy or resume therapy with conventional fat emulsions at 1 gm/kg in addition to the Omegaven® so that additional parenteral fat calories can be given. The clinical team, in conjunction with the patient's primary physician, will determine if the patient should be removed from the protocol.

As previously mentioned, Omegaven® may be infused in the same manner as conventional fat emulsions through either a central or peripheral line. The emulsion is isotonic. It is compatible with parenteral nutrition solutions and may be co-infused via y-site. Omegaven® may be infused through a 1.2micron inline filter.

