# **Data Collection Methods/Assessment and Schedules**

Data will be collected by the PI and the co-investigators. Hospital charts will be reviewed for pertinent clinical information. Results of liver biopsies and blood chemistries will be obtained from the Cerner Power Chart computer system. Specifically, the history of present illness, past medical history, and birth history, pertinent physical exam findings including patient weight, the results of liver biopsies, and parenteral and enteral feeding history will be collected. The information will be recorded on hard copy data collection forms.

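### The essential fatty acid outcome credits every normal profile to Omegaven, although the protocol allows other fat sources that could produce the same result

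*Protocol*

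**What the plan says.** The second aim in the Protocol, *Specific Aims/Objectives*, is "To determine the impact of Omegaven® on the prevention of essential fatty acid deficiency". The matching secondary outcome, in *Definition of Primary and Secondary Outcomes/Endpoints*, is "Omegaven® will prevent EFA deficiency as evidenced by normal EFA profiles on monthly evaluations". Both attribute the result to the drug, and neither mentions other fat.

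Elsewhere the Protocol describes other fat sources during treatment:

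- *Details of Omegaven® Administration*: "If additional fat calories are needed, they will be provided via the enteral route".
- The same section, for a child who cannot get adequate calories parenterally and does not tolerate feeds, lists as an option to "resume therapy with conventional fat emulsions at 1 gm/kg in addition to the Omegaven".
- *Patient Selection and Inclusion/Exclusion Criteria* defines dependence on parenteral nutrition (PN) as being "unable to meet nutritional needs solely by enteral nutrition", so a child on partial feeds qualifies.
- *Duration of Therapy*: "Patients will complete the study when he/she is completely off PN". *Potential Benefit of Omegaven® Treatment* also foresees enteral feeding being advanced while PN continues.

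*Study Design* describes a non-randomized, open-label study and no concurrent control group. *Data Collection Methods/Assessment and Schedules* says that "parenteral and enteral feeding history will be collected", but nothing links this history to the EFA outcome.

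**The concern.** EFA status is worth measuring here because the omega-6 source is taken out of the PN. The preliminary-studies section notes that doing so was expected to cause deficiency, and it answers from another hospital's experience that "the use of Omegaven® as monotherapy does not result in the development of essential fatty acid deficiency". The informative question is whether Omegaven suffices when little or no other fat is given.

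The outcome as worded does not separate that situation from Omegaven plus feeds, or Omegaven plus conventional emulsion. A child whose EFAs come partly or mostly from elsewhere counts as evidence for the drug. With no control group, no comparison corrects this. A conclusion that Omegaven prevents deficiency could then be carried over to children with no other fat source, who are the ones at risk.

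**Working it through.** The Protocol states no EFA success rate, margin or sample-size calculation for this outcome, so there is no figure to reproduce. The check has two parts.

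**1. Does the outcome rule exclude the alternative explanation?**

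- Outcome: a normal profile counts as prevention by Omegaven, with no restriction on draws or patients.
- Enteral fat is allowed, when extra fat calories are needed.
- Conventional emulsion with Omegaven is allowed as an option. Removing such a child from the protocol is left to the clinical team's judgement, so draws on combined fat can stay in.
- Partial feeding at entry is allowed.
- The enteral share must rise in any child who weans, because participation ends when PN stops.
- Comparator: none concurrent.

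The rule therefore excludes none of these sources. Additional EFAs, to the extent absorbed, can only move a profile away from deficiency, so the error has one direction. With 20–25 patients planned (*Recruitment Methods*), each child is 1/25 = 4% to 1/20 = 5% of the sample.

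**2. Could other fat matter against what Omegaven supplies?** (scale only)

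Inputs: goal dose of 1 g/kg/day and added conventional emulsion at 1 g/kg (*Details of Omegaven® Administration*); 10 g fat per 100 mL, linoleic figure 50 for Intralipid and 0.1–0.7 for Omegaven, arachidonic figure 0.1–0.4 for Omegaven (Table 1). The Omegaven figures stand under a percent-of-fat label but may be g/100 mL. The upper values listed for its fatty acids sum to 0.7 + 0.2 + 2.8 + 3.1 + 0.4 = 7.2. That fits 10 g of fat per 100 mL better than 100% of an oil described as mainly omega-3. Both readings are shown.

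| Source | Read as g/100 mL | Read as % of fat |
|---|---|---|
| Omegaven linoleic, 1 g/kg = 10 mL/kg | 10 mL × 0.1–0.7 g/100 mL = 10–70 mg/kg/day | 1 g × 0.1–0.7% = 1–7 mg/kg/day |
| Omegaven arachidonic | 10 mL × 0.1–0.4 g/100 mL = 10–40 mg/kg/day | 1 g × 0.1–0.4% = 1–4 mg/kg/day |
| Conventional emulsion linoleic, 1 g × 50% | 500 mg/kg/day | 500 mg/kg/day |
| Linoleic ratio, conventional to Omegaven | 500/70 to 500/10 = about 7 to 50 | 500/7 to 500/1 = about 71 to 500 |

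The documents give no composition for enteral fat. Assuming 10–20% linoleic acid, the enteral fat that matches Omegaven's linoleic supply is 10/0.20 to 70/0.10 = 50–700 mg/kg/day (0.05–0.7 g/kg/day) on the first reading. On the second it is 1/0.20 to 7/0.10 = 5–70 mg/kg/day (0.005–0.07 g/kg/day).

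These are amounts given, not absorbed, and matching linoleic intake is not the same as explaining a normal profile. They show only that other fat is not negligible beside the drug.

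**The case against.** The strongest reply is that the trial tests a swap of intravenous lipid within usual care, and feeding is part of usual care. Neither the aim nor the outcome says sole fat source, the monotherapy sentence is background, the analysis is left to the statistician, the feeding history is collected, and the study does not aim at statistical significance. An analysis plan that is not shown might split the draws.

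Much of this stands. EFA status on an Omegaven-containing regimen is a legitimate thing to report, and how to tabulate it can be left to an analysis plan. But the Protocol itself fixes the inference that a normal profile shows prevention by Omegaven. A later table does not alter that wording.

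Three stronger readings are tempting and are not supported:

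- *That feeding advances throughout the study by design.* The eligibility section lists enteral advancement among therapies that must already have failed, and the background remarks concern PN care in general. On-study enteral fat is conditional, and some children are foreseen as not tolerating feeds. Only children who wean must have a rising enteral share.
- *That fed children do not depend on Omegaven for EFAs.* No on-study intake is given. The summary credits Omegaven's small arachidonic acid content with preventing deficiency, the preliminary mouse work reports reversal of deficiency on Omegaven, and the background describes patients who absorb enteral nutrients poorly.
- *That the linoleic figures measure the bias.* They ignore arachidonic acid and absorption, and they rest on a unit that is uncertain tenfold and on an assumed enteral composition.

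**Conclusion.** The point holds as a fault in a stated attribution rule. Following the outcome as written can credit Omegaven with normal profiles that feeds or added conventional emulsion supplied, and the bias runs towards success. Its size cannot be derived: the documents show that this can happen, not how often.

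The conclusion rests on the text alone. It does not depend on the assumed enteral composition or on how the unit in Table 1 is read; on either reading, conventional emulsion at 1 g/kg supplies at least about 7 times Omegaven's linoleic acid. Because this is a secondary outcome, the change should be made, but the primary outcome is unaffected.

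**What to change.** From the parenteral and enteral feeding history, classify each EFA draw by whether Omegaven was the only meaningful fat source. That means no conventional emulsion, and enteral fat below a cut-off in g/kg/day fixed before the data are examined. Then:

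1. Base the statement that Omegaven prevents deficiency on those draws.
2. Report the other draws separately, as Omegaven plus other fat.
3. Describe the all-draws result as EFA status on an Omegaven-containing regimen, and reword the outcome to match.

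A split on enteral fat alone would not do. The children considered for added conventional emulsion are those who do not tolerate feeds, so they would fall into the supposed sole-source group while receiving the larger linoleic source.

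The cost is one derived variable and a split table, with no change to treatment, feeding, visits or blood draws. Fewer draws will support the sole-source statement, and they will be selected by intake after baseline, so the number of children and draws in each group should be shown. The history comes from chart review, so enteral fat may be only roughly quantifiable, especially for outpatients. Draws that cannot be classified should be reported as such.

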#### **Dose Modification**

Hypertriglyceridemia:

If hypertriglyceridemia develops, defined as serum triglyceride levels > 200 mg/dL, the following will be considered prior to reducing the dose:

- a) If the level was obtained while the patient was receiving a continuous 24- hour infusion of Omegaven®, the total dose should be infused over 20 hours, and a repeat serum triglyceride level obtained prior to resuming the infusion 4 hours later.
- b) Other sources of hypertriglyceridemia should be considered and addressed (drugs, renal disease)

If necessary, if the triglycerides continue to remain high despite the aforementioned interventions, a dosage reduction of 25% will be considered.

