#### Overdose:

In the event of an overdose of Omegaven®, there is a risk of developing fat overload syndrome that may occur when the triglyceride level rises >200 mg/dL acutely as a result of too rapid a rate of infusion, or chronically at high infusion rates in associated with a change in the patient's clinical condition (e.g., renal dysfunction, sepsis). In such cases, the infusion should be stopped or, if necessary, continued at a reduced dose.

Metabolic acidosis has occurred in patients receiving Omegaven® at excessive doses without simultaneous administration of dextrose.

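### The triglyceride outcome counts only levels above 400 mg/dL, although the protocol defines and manages hypertriglyceridemia from 200 mg/dL, so the reported rate mixes the drug with the management rule

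*Protocol*

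**What the plan says.** Under Definition of Primary and Secondary Outcomes/Endpoints, the triglyceride outcome is: "The rate of triglyceride levels > 400 mg/dL with Omegaven® will be similar to that seen with PN administered with soy oil IFE". The evidence for it is described as "as evidenced by baseline data and then weekly and monthly evaluations". No other triglyceride outcome is listed, although Specific Aims/Objectives names the effect on serum triglyceride as an aim in general terms.

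Elsewhere the working threshold is 200 mg/dL:

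- **Dose Modification:** "If hypertriglyceridemia develops, defined as serum triglyceride levels > 200 mg/dL, the following will be considered prior to reducing the dose". Step (a) applies on the condition "If the level was obtained while the patient was receiving a continuous 24- hour infusion of Omegaven", and then "the total dose should be infused over 20 hours, and a repeat serum triglyceride level obtained prior to resuming the infusion 4 hours later". Step (b) is a search for other causes. If levels stay high, a 25% reduction is to be considered.
- **Data and Safety Monitoring Plan:** a dose reduction at the same 200 mg/dL level is stated as something that happens, not as an option.
- **Overdose:** refers to "fat overload syndrome that may occur when the triglyceride level rises >200 mg/dL acutely".

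The protocol does not explain why the outcome uses 400 when the definition and the actions use 200.

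**The concern.** Treatment may be changed at half the level that counts as an event. A child whose level reaches 300 mg/dL meets the protocol's own definition and comes under the management steps, yet adds nothing to the outcome unless some level passes 400. The rate above 400 is thus a property of the emulsion and of how elevations are handled, taken together.

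That matters because the outcome is a comparison. The study has one arm, and the soy oil rate is to come from baseline data. The protocol does not say whether triglycerides above 200 mg/dL on soy oil were managed by the same rule. If they were not, a similar or lower rate on Omegaven could partly reflect the rule, and a reader could take it as evidence of lipid tolerance. The aim on serum triglyceride would then rest on an outcome that omits the range in which the protocol itself sees a problem.

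**Working it through.** The protocol gives no expected triglyceride rate, standard deviation, margin or power, so there is no figure to reproduce. The check compares the sections and then illustrates direction and precision on assumed inputs.

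**1. Thresholds**

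| Use | Level | Section |
|---|---|---|
| Definition | > 200 mg/dL | Dose Modification |
| Management steps, reduction considered | > 200 mg/dL | Dose Modification |
| Dose reduction stated as occurring | > 200 mg/dL | Data and Safety Monitoring Plan |
| Link to fat overload syndrome | > 200 mg/dL | Overdose |
| Outcome event | > 400 mg/dL | Primary and Secondary Outcomes |

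400 / 200 = 2: the event threshold is twice the action threshold.

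**2. What the outcome leaves out (assumed counts).** Suppose 6 of 20 children pass 200 mg/dL and 1 of them passes 400. The proportion meeting the protocol's definition is 6/20 = 30%. A patient-level version of the outcome shows 1/20 = 5%.

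**3. Direction (simulation, all inputs assumed).** Triglycerides were log-normal with 20 weekly draws and lag-1 correlation 0.5. Three scenarios were used: median 120 with between- and within-child log-SD of 0.4; median 150 with 0.4; median 150 with 0.5. Under the rule, a level above 200 leads to a repeat at 0.5, 0.7 or 0.9 of its value. If the repeat is still above 200, later levels are multiplied by 0.90 or 0.75.

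Share of children with any weekly level above 400 (repeats not counted):

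| Scenario | No rule | Repeat × 0.9 | Repeat × 0.7 | Repeat × 0.5 |
|---|---|---|---|---|
| 120, 0.4 | 13.3% | 3.3–6.4% | 7.1–10.0% | 13.7% |
| 150, 0.4 | 26.7% | 7.6–13.0% | 13.4–18.9% | 26.7–26.8% |
| 150, 0.5 | 42.2% | 18.9–28.4% | 27.7–35.0% | 41.8–42.0% |

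Within each range, the lower end generally goes with the larger reduction. The rate falls when the rule triggers an effective change. It is essentially unchanged when the repeat is so low that a change rarely follows. With no effect of the dose change (factor 1.0), the share also stays put: 13.8–14.0%, 26.5–27.1% and 41.6–41.8%.

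**4. The repeat draw on its own.** With no dose effect and the repeats counted in a per-level rate, that rate moves from 1.6% to 1.5–2.3%, from 4.1% to 3.3–5.3%, and from 8.3% to 6.8–10.8% in the three scenarios. The effect goes both ways.

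**5. Precision at the planned size.** Recruitment Methods plans 20–25 children. If none passes 400, the one-sided 95% upper limit is 1 − 0.05^(1/n), which is 13.9% for n = 20 and 11.3% for n = 25. If the true proportion were 10%, the chance of seeing none is 0.9^20 = 0.12 or 0.9^25 = 0.07. A rate of zero would be limited reassurance even without the management rule.

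**The case against.** A low threshold for precaution and a higher one for marked elevation are not a contradiction; counting marked elevations under treatment as managed is a legitimate target. The Dose Modification steps are to be considered, so little may change in practice. Episodes above 200 mg/dL are not lost either. The table of possible adverse events lists hypertriglyceridemia as Grade I, and the adverse event section requires the action taken with study medication to be recorded. The outcome is secondary, in a small study that disclaims any aim of statistical significance. All of this stands, and it makes the point minor. It does not give the outcome section a measure at the protocol's own definition, and it does not show that the soy values were managed alike.

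A reader might infer two stronger things that the document does not support.

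- **That the rules force the rate to zero and make the outcome uninformative.** They do not. The actions in Dose Modification are discretionary, levels are drawn at intervals, and a value already above 400 counts.
- **That the repeat level after the 4-hour break dilutes the rate.** The outcome rests on weekly and monthly evaluations, whereas this repeat is drawn for cause. It applies only to levels taken during a continuous 24-hour infusion, while the protocol allows 12 to 24 hours. Nothing says it enters the rate, and step 4 shows that its effect would be mixed if it did.

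**Conclusion.** The threshold mismatch is in the text and needs no assumption: the outcome omits all 200–400 mg/dL episodes and describes Omegaven together with the management rule. That the rate is lowered is conditional on the actions at 200 mg/dL being taken and being effective. That the soy comparison is distorted is conditional on the soy values having arisen under different management, which the protocol leaves open. The size cannot be derived from the document; the simulated figures show direction only. Severity is minor. The primary outcome is unaffected, and the adverse event record may hold the missing episodes.

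**What to change.** In Definition of Primary and Secondary Outcomes/Endpoints:

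1. Keep levels above 400 mg/dL as a severe tier.
2. Add the proportion of children with any scheduled level above 200 mg/dL, the Dose Modification definition. Apply both tiers in the same way to the soy baseline values, and state how those values were obtained and managed. Give the number of levels per child in each period, because the chance of any exceedance grows with the number of draws.
3. Report beside it the number of children whose infusion time or dose was changed because of triglycerides.
4. Base the rate on the scheduled draws and leave out the for-cause repeats under Dose Modification step (a).

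The rate should not be limited to levels drawn during infusion. The draw condition of the soy values is not stated, and such a limit could create a new imbalance.

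No treatment rule changes. Separately, Dose Modification (reduction considered) and the Data and Safety Monitoring Plan (reduction occurs) differ and must be reconciled.

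The cost is outcome wording and a tabulation. Triglycerides are already in the laboratory schedule at every stage, and action on study medication is already recorded for adverse events. The downside is that the reported rate will look less favourable.
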